*Aim 1: Evaluate the impact of the Partnership enhancements in increasing the number of students and families receiving services and expressing satisfaction with them.* For this primary aim, and per experiences from prior RCTs (18,19), as mentioned, we will collect data for each student on the number of sessions conducted by the SBH clinician in categories of assessment; individual, group and family therapy; case management; and teacher consultation. In addition, during the COVID-19 school closure period we will document which students receive any of these services through telehealth, and will document this form of service received. This will enable coding of overall productivity, for types of services, and for family involvement in care. To measure satisfaction with services, at the three month or case closure assessment points, we will collect the Client Satisfaction Questionnaire-8 (CSQ-8) from students and parents. The CSQ-8 is a brief, widely used 8-item measure for use with youth aged 11 and older and adults (50).

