*Aim 2: Evaluate the impact of the Partnership enhancements on students' social, emotional/behavioral (EB), and academic outcomes.* For this primary aim, there will be two sub-aims: Aim 2a will evaluate the impact of the Partnership enhancements on school-wide academic record variables of grades, attendance, lateness and discipline referrals. Aim 2b will focus on students receiving Tier 3 services and will assess their social and emotional/behavioral (EB) functioning. To assess social functioning, the Child and Adolescent Social and Adaptive Functioning Scale (51) will be completed by students. The CASAFS includes 24 items measuring students' functioning in four key social roles: school performance, peer relations, family relations, and home duties/self-care. Additionally, both "internalizing" EB problems, which include problems of depression, anxiety and exposure to trauma, and "externalizing" EB problems, which include conduct and attention problems, will be measured for students receiving Tier 3 services. Student EB functioning will be measured by parent and student report forms of the Brief Problem Checklist (52), a 12-item questionnaire that measures externalizing and internalizing problems. Derived from the comprehensive Child Behavior Checklist (53), it is designed for repeated periodic assessment of clinical progress, yielding both an internalizing and externalizing subscale (52). Please note that academic variables collected above school-wide for stream 1 data collection, will also be used for stream 2 data collection for students receiving Tier 3 services. Changes in the above variables will be assessed for students for the academic quarter before receiving mental health services and the academic quarter after services have been completed.

*Additional Measures.* In addition to measures directly reflecting study aims, secondary aims will be addressed by measures reflecting the potential impact of the two Partnership enhancements will be collected at the same time intervals for students receiving Tier 3 services. For the enhancement focused on mental health education and stigma reduction, students will complete The Guide Curriculum Assessment (GCA) reviewed previously (43,44). The GCA includes subscales assessing Mental Health Literacy in three dimensions: Mental Health Knowledge (MHK; 28 items),

PRINCIPAL INVESTIGATOR: [name]

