A priori power analyses indicate that we will be adequately powered to detect any primary outcome that has an effect size of  $d=.29$  or greater (i.e., between small [ $d=.2$ ] and medium [ $d=.5$ ] in size per Cohen, 1988). Statistical software does not differentiate between one variable (e.g., depression) or another (e.g., anxiety) when executing power analysis for an outcome. Notably, Ferguson (2009) recommends that "minimum effect size representing a 'practically' significant effect for social science data" with difference measures like Cohen's  $d$  is .41.

Variation in cluster size is a typical (and expected) occurrence in cluster-randomized trials, with a priori power analyses invoking the projected average sample size per cluster for projected MDES estimates to accommodate differences in cluster size. Moreover, methodological literature has shown that any negative influence of cluster imbalance is limited to situations where there is a severe Pareto imbalance, defined as "a situation in which 80% of the subjects actually belong to only 20% of the clusters" (Guittet, Ravaud, & Giraudeau, 2006). This is not the situation here, and thus we expect the observed imbalance to have a negligible impact on analyses. Power analysis for the study corresponds to the ITT effect of the intervention, wherein the probability of the intervention's ability to reject a null-hypothesis of no intervention effect is considered. Power estimates are not provided for the dose-response effect (i.e., the effect of treatment at varying dose levels) as this will be calculated using a Bayesian method (i.e., Bayesian Additive Regression Trees, BART).

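### Both aims are called primary and list about 13 measures, but the plan names no primary endpoint, alpha or success rule and has no multiplicity control

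*Combined protocol and SAP*

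**What the plan says.** The Measures and Measurement Plan introduces Aim 1 as primary: "For this primary aim, and per experiences from prior RCTs (18,19), as mentioned, we will collect data for each student on the number of sessions". The aim itself is to "Evaluate the impact of the Partnership enhancements in increasing the number of students and families receiving services and expressing satisfaction with them". Session data are to be used broadly: "This will enable coding of overall productivity, for types of services, and for family involvement in care". For satisfaction, "we will collect the Client Satisfaction Questionnaire-8 (CSQ-8) from students and parents".

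Aim 2 is also introduced as a primary aim and is split in two. "Aim 2a will evaluate the impact of the Partnership enhancements on school-wide academic record variables of grades, attendance, lateness and discipline referrals". Aim 2b covers Tier 3 students: "To assess social functioning, the Child and Adolescent Social and Adaptive Functioning Scale (51) will be completed by students", and "Student EB functioning will be measured by parent and student report forms of the Brief Problem Checklist", which gives an internalizing and an externalizing subscale. The academic variables are used again for Tier 3 students. Measures of the two enhancements themselves are placed under secondary aims.

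Power considerations (Analytic Plan) refers to primary outcomes without listing them. It gives a minimum detectable effect size (MDES) of .29 at N = 1225 and .28 at N = 1400, with 22 schools, 30% of variance explained and 80% power. It then says: "A priori power analyses indicate that we will be adequately powered to detect any primary outcome that has an effect size of" d = .29 or greater.

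In the available text, neither the Analytic Plan nor any other section gives an alpha, sidedness, ranking of outcomes, preferred informant, success rule or adjustment for multiple outcomes. The 250 Monte Carlo simulations check the Bayesian Additive Regression Tree (BART) models. They do not limit error across outcomes in the two-level comparisons.

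**The concern.** The plan separates primary from secondary aims but does not say which outcome within a primary aim carries the conclusion. Its power figure applies to one test at a time. Yet the Background section poses a single decision: whether efforts on these two enhancements are worth making. If about 13 outcomes are tested at an unadjusted level and the emphasis is settled after results are seen, the error rate behind that decision is well above that of a single test. A choice of endpoint made after the data are seen cannot be credibly repaired later.

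**Working it through.** **1. The plan's own MDES.** Inputs from the Analytic Plan: J = 22 schools, 11 per arm; N = 1225 (n = 1225/22 = 55.7 per school); R² = .30; power 80%. Alpha and the intraclass correlation (ICC) are not given. I assume two-sided .05, 19 degrees of freedom and R² = .30 at both levels, and solve for the ICC.

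MDES = (t[.975] + t[.80]) × √{(1 − R²) × [ICC/(.25J) + (1 − ICC)/(.25Jn)]}

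With ICC = .057: (2.093 + .861) × √{.70 × [.057/5.5 + .943/(5.5 × 55.7)]} = 2.954 × .0970 = .287. At N = 1400 the same formula gives .282. These round to the stated .29 and .28, so the figure is plausible for one test at an unadjusted .05.

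**2. Count of comparisons** (Measures and Measurement Plan):

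- Aim 1: number receiving services, overall sessions, CSQ-8 student, CSQ-8 parent = 4
- Aim 2a: grades, attendance, lateness, discipline = 4
- Aim 2b: CASAFS total 1, plus Brief Problem Checklist 2 subscales × 2 informants = 5

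The total is 13. One informant for the CSQ-8 and the checklist removes 1 + 2, leaving 10. Adding the four academic variables in Tier 3 students gives 17. Separate service categories or CASAFS roles would add more.

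**3. Chance of at least one false result, all nulls true, each test at two-sided .05.** If independent, the chance of a false difference in either direction is 1 − .95^k; favouring Partnership only, it is 1 − .975^k. For k = 13: 1 − .95^13 = .487 and 1 − .975^13 = .280. Correlated cases come from simulating equicorrelated normal statistics (400,000 draws).

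| Tests | Correlation | Either direction | Favouring Partnership |
|---|---|---|---|
| 1 | – | 5% | 2.5% |
| 10 | 0 | 40% | 22% |
| 10 | .5 | 29% | 14% |
| 13 | 0 | 49% | 28% |
| 13 | .3 | 42% | 21% |
| 13 | .5 | 33% | 17% |
| 17 | 0 | 58% | 35% |
| 17 | .5 | 39% | 19% |

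Within a single aim, 4 to 5 tests give about 16–23% in either direction (correlation .5 to 0).

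**4. Effect on the MDES of three named endpoints.** Holm's strictest step uses .05/3. Only the t multiplier changes: .29 × (2.625 + .861)/(2.093 + .861) = .29 × 3.486/2.954 = .342. For comparison, Bonferroni over all 13 gives about .41.

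**5. Why .34 is not a common figure.** The .29 is built on N = 1225, which the Recruitment Plan gives as the Tier 3 consent target. Aim 2a uses school-wide records, and the Recruitment Plan puts that population at about 12,000 in Year 1 and 20,000 overall. With the same assumed ICC of .057, the formula in step 1 gives about .25 to .26 unadjusted and about .30 at .05/3. A different ICC for academic records would change this. The number of students served is naturally a count per school, and absences and referrals are to be modelled with a zero-inflated Poisson link. A student-level d does not carry over to either.

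**The case against.** The documents list measures, not tests, so 13 is a count under an assumption and not a floor; one informant gives 10. This stands, but the error rate is still well above nominal at 10.

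A reader might infer that the 33–49% is the chance of a false conclusion that Partnership works. Under two-sided tests it is not: that range includes false differences favouring Wellness, and the pro-Partnership part is 17–28%. One-sided tests at .05 would give 28–49% for a false pro-Partnership result (correlation .5 to 0). The Outcomes section states a directional hypothesis, but no section says that the tests are one-sided.

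A reader might also infer that any one significant outcome would count as success. The documents do not say so. In context, the phrase about any primary outcome means that the MDES applies whichever outcome is considered, and the Outcomes section expects improvement in several domains together. The supportable criticism is that no success rule is stated.

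Finally, Aims 1, 2a and 2b ask different questions, partly in different populations, so sharing one .05 among them is a choice. That is fair. It does not answer the 4 to 5 unranked tests within each aim, nor the single decision posed in the Background. Naming one endpoint per aim is the essential repair; Holm across the three is a modest addition.

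**Conclusion.** The gap is real and should be closed. With 13 tests, the chance of at least one false difference is about 33–49%, and of a false result favouring Partnership about 17–28%. That is roughly 7 to 10 times the 5%, and 7 to 11 times the 2.5%, of a single test. These figures assume two-sided .05, every null true, correlations of .5 to 0, separate tests for each informant and subscale, and tests that hold their nominal size with 22 schools. None of these is fixed by the plan. A higher correlation lowers the risk without removing it: at .7 the two figures are 24% and 12%. The absence of a rule is judged on the text available.

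**What to change.** Before any arm comparison is run:

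- In the Measures and Measurement Plan, name one primary endpoint and one informant (where informants apply) for each of Aims 1, 2a and 2b. Label all other outcomes secondary.
- In the Analytic Plan, state alpha and sidedness, and test the three endpoints with Holm at overall two-sided .05.
- In Power considerations, replace the reference to any primary outcome with the three named endpoints, and restate the MDES for each from its own sample, unit and model. For a continuous student-level Tier 3 endpoint with N = 1225, .29 becomes about .34. Aim 2a and any count-type endpoint need their own figures, with the assumed ICC stated.

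The cost is wording only, with no new data. The stated MDES becomes slightly less favourable, though .34 is still below the .41 that the plan itself cites as practically significant.

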**Analytic Plan.** The proposed project is a cluster-randomized controlled trial (J=22 schools; 11 per treatment arm) comparing the efficacy of Wellness vs. Partnership services. As a general analytic plan, we will use hierarchical linear modeling (HLM) to evaluate the project aims. Specifically, we will use two-level HLM models to account for students being nested within schools. Though one might conceptualize this proposal as a three-level model (i.e., students nested within schools, and schools nested within sites), it would be neither feasible nor recommended to model site as a multilevel variable given there are only two sites in the design (56). In line with best practice, we will integrate site (i.e., SC vs. MD) as a covariate in the statistical models to contain any potential effects of this variable. Based on prior research conducted by the team, we expect intraclass correlations (ICCs) to warrant the incorporation of random intercepts to account for violations of independence. We will also test independence assumptions for the treatment parameters to determine how sensitive treatment effects are to potential violations of independence, and will include random slopes to account for nested treatment effects if ICCs exceed .01. For transparency, we will report both fixed and random effects (i.e. intercepts and slopes) of the model. Additionally, we will iteratively subset the model using a k-1 sensitivity analysis to determine the influence of individual sites on parameter estimates. We will estimate statistical models using full information maximum likelihood to accommodate any missing data (57). We will use maximum likelihood with robust standard errors to estimate models that include the Zero Inflated Poisson link function for count

PRINCIPAL INVESTIGATOR: [name]

outcomes (e.g. absences, referrals). This general analytic framework will be used in aims 1 and 2. Details, exceptions, and modifications to it are discussed below.

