Given the experiment will examine intent-to-treat effects in a real-world setting, we will conduct analyses to investigate variability in implementation and compliance to enhance causal effect interpretation of clients "as treated." Specifically, we will use a Bayesian Additive Regression Tree approach (BART; 61) to delineate the impact of key treatment assumptions (e.g., compliance, fidelity, etc.), as well as to estimate the impact of assumption violations on the estimation of causal effects in the design. BART is an extension of Classification and Regression Tree (CART) models that is based on a recursive partitioning algorithm that explains variation in the outcome through repeated splits of the data into homogenous subgroups that are similar on predictor variables. One significant strength of BART is that it is capable of handling a large number of predictors and incorporates higher-order interactions that may be excluded from parametric analysis. Research indicates that BART is insensitive to tuning parameters and produces more accurate estimates of treatment effects compared to other methods of analyzing treatment effect heterogeneity (i.e., propensity score matching, propensity-weighted estimators, instrumental variable procedures, and regression adjustment; 61). Note that this BART enhancement to the randomized, experimental design should not be mistaken for a Bayesian trial design.

*Power considerations.* The design originally included a planned sample size of approximately N=2800 (1400 per arm) for Aims 1 and 2. We previously revised power estimates for these study aims that consider the possibility of reduced participant involvement given COVID-19 and recruitment challenges more broadly, with a revised sample size of approximately N=1400 (700 per arm). With the research study period concluding in June 2023, we have revised the enrollment projection to a conservative estimate of N=1225. With our currently active sites (J=22) and the total number of students enrolled in the study (N=1225, including expected spring 2023 enrollment), assuming 30% of variance

PRINCIPAL INVESTIGATOR: [name]

explained in the primary outcomes by pre-test covariates, and 80% power, we have a minimum detectable effect size (MDES) of .29. If we reach our goal of 1400 students, we will be at .28.

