*Study retention.* Due to documented accessibility advantages of SBH (16) and our past experiences, Tier 3 students and parents are likely to remain involved in the study throughout the span of treatment. Additionally, the intervention requires no extra effort to participate outside of the assessments, with similar types of assessments routinely used in treatment for progress monitoring. In similar studies conducted, the most common reason for study attrition was due to students transferring to another school, which has been nominal across school wide populations. However, Tier 3 students experiencing EB problems are more likely to transfer schools than the general population.

*Incorporating research activities into routine care.* All research activities will be included in routine SBH functions. Consent to participate will be integrated into the existing process that clinicians use to obtain consent for treatment. Students and their parents may notice that their clinician is utilizing some new strategies, however all within parameters of expected clinical care. The same is true in the Partnership condition, will all enhancements those that would logically occur in a school embracing innovation and pursuing holistic strategies to remove barriers to student learning.

*Training and experience of recruitment personnel.* For students receiving Tier 3 services, the 20 clinicians will assist in study recruitment. Beginning in Year 2, a clinician was added in two [REDACTED] schools, one per condition for a total of 22 clinicians. Beginning in Year 3, two additional schools were added, one per condition, for a total of 22 schools and 24 clinicians. All clinicians will have a master's degree in a behavioral health discipline (e.g., psychology, counseling, social work) and will hold a valid license to provide psychological services or be under the supervision of a licensed clinician. Each clinician will participate in human subjects training prior to recruitment efforts and will be trained by the research team on recruitment procedures. The Lead Research Manager, [name], will oversee recruitment efforts with the PI, [name] and Co-I/MD Site PI, [name], as guided by the SAB and building on experiences from prior RCTs conducted

PRINCIPAL INVESTIGATOR: [name]

by the research team, including a large current RCT funded by the National Institute of Justice that includes an opt-out procedure. See below for recruitment parameters.

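### One MDES of .29 is claimed for every primary outcome, but in a trial of 22 randomised schools it depends on each outcome's ICC and covariate R², which are not given by outcome

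*Combined protocol and SAP*

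**What the plan says.** The Analytic Plan describes a "cluster-randomized controlled trial (J=22 schools; 11 per treatment arm") analysed with two-level models, and says of clustering that "we expect intraclass correlations (ICCs) to warrant the incorporation of random intercepts". It gives no ICC value there beyond .01, which is a trigger for adding random slopes.

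Under *Power considerations* the inputs are 22 schools, "the total number of students enrolled in the study (N=1225, including expected spring 2023 enrollment"), 30% of outcome variance explained by pre-test covariates, and 80% power. The result is stated as "and 80% power, we have a minimum detectable effect size (MDES) of .29", falling to .28 at 1,400 students. The next paragraph generalises it: "we will be adequately powered to detect any primary outcome that has an effect size of" d = .29 or more. The reason offered is "Statistical software does not differentiate between one variable (e.g., depression) or another (e.g., anxiety) when executing power analysis for an outcome".

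The measures under the primary aims are unlike one another:
- Aim 1: session counts and the CSQ-8, the latter collected at three months or case closure.
- Aim 2a: school-wide grades, attendance, lateness and discipline referrals.
- Aim 2b: the CASAFS and the Brief Problem Checklist. For Tier 3 students the plan analyses difference scores.

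Count outcomes, with absences and referrals as the examples, are to be fitted by a zero-inflated Poisson model.

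**The concern.** Software returns the same standardised MDES for two outcomes only if they are given the same inputs. In a school-randomised design those inputs include the outcome's own school ICC and the share of variance that covariates remove at each level. With only 22 schools, the ICC term dominates. Because the ICC is not reported, a reader cannot tell for which outcomes .29 holds.

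The plan itself gives reasons to expect the inputs to differ. An outcome with no pre-test cannot draw its 30% from a pre-test of itself. Recruitment is described as ending "for a total of 22 schools and 24 clinicians", so clinician differences in sessions delivered or in satisfaction are nearly inseparable from school differences. The documents do not say how large those differences are.

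The stake is interpretation. The decision the trial is meant to inform is whether the Partnership enhancements are worth the effort or unnecessary. If .29 is taken to hold for every primary outcome, a null on satisfaction or service use could be read as adequately powered when it was not.

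**Working it through.** **Inputs from the plan.** J = 22 schools, 11 per arm; N = 1,225; R² = .30, level not stated; power 80%; stated MDES .29 (.28 at N = 1,400).

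**Assumptions.** Two-sided alpha .05, 20 degrees of freedom, equal school sizes. The ICC, written ρ, is unknown.

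**Formula.** MDES = M × √[(4/22) ρ (1 − R²school) + (4/N)(1 − ρ)(1 − R²student)], with M = t(.975, 20) + t(.80, 20) = 2.086 + 0.860 = 2.946.

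**Step 1: the plan's figure.** It cannot be computed forward without ρ, so solve back. The bracket must equal (.29 / 2.946)² = .00969.

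- 30% at student level only: .18182ρ + .00229(1 − ρ) = .00969, so ρ = .041.
- 30% at school level only: .12727ρ + .00327(1 − ρ) = .00969, so ρ = .052.
- 30% at both levels: .12727ρ + .00229(1 − ρ) = .00969, so ρ = .059.

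As a check, ICCs of .040, about .050 and .057 to .058 respectively return both stated figures after rounding (.29 at 1,225 and .28 at 1,400). A single unreported ICC of roughly .04 to .06 therefore probably lies behind them. The .01 in the Analytic Plan cannot be the input, since it gives about .18 to .20.

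**Step 2: outcomes with no pre-test.** Keep those three ICCs and set R² = 0 at both levels, the limiting case for CSQ-8 and session counts.

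| ICC | Bracket | MDES | Power at d = .29 |
|---|---|---|---|
| .041 | .0106 | .30 | 76% |
| .052 | .0125 | .33 | 69% |
| .059 | .0138 | .35 | 65% |

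Power is from the noncentral t with 20 df. With R² = 0, .29 is reached only at ICC .036 or below.

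**Step 3: dependence on the ICC.** The ICCs are assumed and the plan's other inputs held. Each pair is R² = .30 at both levels / at student level only.

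| ICC | MDES | Power at d = .29 |
|---|---|---|
| .02 | .20 / .23 | 98% / 95% |
| .05 | .27 / .31 | 85% / 74% |
| .10 | .36 / .42 | 62% / 49% |
| .15 | .43 / .50 | 48% / 37% |

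**Step 4: dependence on school-level R².** With student R² at .30 and an assumed school R² of .50 or .70, the ICC at which MDES = .29 rises to .084 or .142. The threshold therefore moves with both inputs, and in either direction.

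**The case against.** The strongest reply is that no outcome is shown to exceed the threshold. The documents give no ICC for any measure. At ICC .02 the stated .29 is conservative. That stands. A reader might infer from the .10 and .15 rows that power for satisfaction, sessions or academic records is near a coin flip, but those ICCs are assumed and the documents do not support that conclusion.

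Second, school-level covariates may explain more than 30%. The models adjust for site, which separates urban Maryland from rural and suburban South Carolina, and 2018-19 school-wide records are planned. This also stands. A reader might infer that the much larger school-wide sample cannot help Aim 2a. With 22 × 600 = 13,200 students and an assumed ICC of .10, the same formula gives .33 / .40 under the 30% readings. With student R² at .30, it gives about .28 at an assumed school R² of .50 and .22 at .70. No unconditional statement is warranted.

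Third, the software sentence is true for two outcomes with identical inputs. That is correct. The error lies in extending it to all primary outcomes, not in the sentence read narrowly.

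Fourth, the power text was last revised as enrolment was closing, so no sample-size decision depends on it, and the plan commits to reporting random effects. Both limit the consequence. They do not make the stated property true for outcomes with different inputs. Nor do the unstated alpha and sidedness rescue it: one-sided .05 moves the break-even ICC to about .057 to .082, and the dependence remains.

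**Conclusion.** The concern holds in a limited form. The plan attributes to every primary outcome a detectable effect that its inputs support only for outcomes with a particular unreported combination of ICC and R². Under two-sided .05 and equal school sizes, that combination is an ICC of about .041 to .059 with the plan's 30%, or higher if school-level covariates explain more.

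The clearest case rests on the plan's own measurement schedule. CSQ-8 and session counts have no pre-test. At the ICCs implied by .29, the MDES for them is about .30 to .35 rather than .29, with power of about 65% to 76% at d = .29. This is the R² = 0 limit; site or other baseline variables could recover some of the difference. The wider range by ICC is illustrative.

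This does not establish that the trial is underpowered for any named outcome. Two further limits apply. The plan labels its aims, not individual measures, as primary, so the list of outcomes affected is inferred. Some pages were also removed before review, so unstated means not stated in the text available.

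**What to change.** 1. Delete the sentence about software, and replace the claim for any primary outcome with an MDES for each, after naming which measures are primary.
2. State alpha and sidedness, the ICC, and R² at student and at school level. Show the MDES over a range of ICCs.
3. Use the ICC of the quantity analysed. For the CASAFS and Brief Problem Checklist this is the ICC of the change score, because stable school differences at intake cancel in the difference. For CSQ-8 and sessions, use prior-trial values or a within-arm (treatment-adjusted) ICC. Pooling post-treatment data over arms would put the treatment effect into the between-school variance, adding about d²/4 = .29²/4 = .021. For academic outcomes, use the 2018-19 records with school-level R² where available, checking coverage for the two schools added in Year 3.
4. Give count outcomes as a detectable rate ratio, since a standardised difference is not the scale of the zero-inflated model.
5. Claim .29 only where the outcome's ICC and R² support it.

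The cost is plan wording and some calculation from records, trial data or prior-trial values. No design change is needed. The price is a less favourable stated figure for some outcomes.
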